#### **E. Regulatory Issues: Adverse Events, Serious Adverse Events, Collection and Reporting**

Adverse Events: An adverse event is any unwanted experience or event occurring during the course of a clinical trial. At each visit, either a research nurse or physician will query the participant and log side effects and other treatment emergent events since the past visit, recording their severity (mild, moderate, severe, life-threatening), what action was taken, and whether the symptoms are continuing or resolved. The study investigators will follow all AEs to the point of a satisfactory resolution. A study subject may be withdrawn from the study if the PI determines it is the best decision for protection of the safety of the subject. All AEs will be assessed to determine if they meet criteria for an SAE. AEs will be quantified separately by sex and treatment groups and compared across treatment groups with Fisher's exact test (for binary events) or with chi-square test (for counts of events or event rates). The event will be documented as to whether there is 1) no relationship between the study drug and the adverse event, 2) the adverse event is unlikely related to administration of the study drug, 3) the adverse event is possibly related to study drug administration, or 4) the adverse event is probably related to the administration of the study drug.

Serious Adverse Events (SAE): A serious adverse event is defined as an outcome that is 1) fatal or life-threatening, 2) significantly or permanently disabling or incapacitating, 3) requires or prolongs inpatient hospitalization, or 4) results in

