a congenital anomaly. SAE's, whether or not related to study medication, will be reported to the IRB and NIDA. All drug related adverse events of a non-serious nature are reported to the University of Minnesota's IRB on a quarterly basis. Serious adverse events will be reported by telephone to the IRB, and to NIDA and the FDA within the three days of our receipt of information regarding the event and written reports will be submitted within ten days. If a subject either withdraws from the study or the investigator decides to discontinue a subject due to SAE, the subject will have appropriate follow-up medical monitoring. Monitoring will continue until the problem requiring hospitalization was resolved or stabilized with no further change expected, is clearly unrelated to study medication, or results in death. Outcome of SAEs will be periodically reported to NIDA. A summary of the SAEs that occurred during the previous year will be included in the annual progress report to NIDA. Finally, the PI's will ensure that serious adverse events reported to NIDA via the serious adverse event tracking and reporting system at <https://saetrs.nida.nih.gov/>.

The Principal Investigator will then take appropriate action (including study modification) as agreed upon by these monitoring groups including the DSMB when needed. The Principal Investigator will determine whether the seriousness of the event warrants removal of the participant from the study. Appropriate diagnostic and therapeutic interventions will be initiated and the participant will be medically followed and kept under observation as long as medically indicated. After the review of the data, the DSMB report will make recommendations about whether the trial should continue with or without modifications, or be terminated. Any potential conflict of interest in the Data and Safety Monitoring Board will be disclosed.

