Generic Prometrium, a natural progesterone, is generally well tolerated. The most common adverse effect is sedation. Other less common adverse effects include menstrual irregularity, spotting or breakthrough bleeding, dizziness, cramps, nausea, fatigue, headache and breast tenderness (de Lignieres, 1999; Simon, 1995, Sofuglu, 2009). Other side effects attributed to synthetic progesterone, including depression, fluid retention, pruritus, jaundice, rash and thrombotic disorders, are unlikely to occur. Recently there have been reports of increased risk of stroke, coronary artery disease, venous thromboembolism and breast cancer in postmenopausal females who have been on long-term hormone replacement treatment with estradiol and progestin (medroxyprogesterone) combination (Anonymous, 2002; Grady et al., 2002; Hulley et al., 2002; Nelson et al., 2002). While some of these adverse events develop after years of treatment, venous thromboembolism is seen within the first year of treatment (Anonymous, 2002). It is possible that progestins may contribute to thromboembolism seen during estradiol and progestin treatment and thromboembolism is listed in the PDR as one of the adverse events for medroxyprogesterone treatment (PDR, 2002). In contrast to synthetic progestins, natural progesterone is not known to cause thromboembolism (PDR, 2002). However, as a safety measure for these serious adverse events, we will exclude subjects with history of thrombophlebitis, deep vein thrombosis, pulmonary embolus, clotting or bleeding disorders, heart disease, diabetes or history of stroke. Possible adverse events from generic Prometrium will be assessed weekly by the research nurse ([name], NP) in consultation with the study physicians ([name] MD, [name] MD). If the side effects cannot be tolerated the medication dosage will be decreased to 200 mg daily.

Although uncomfortable, withdrawal symptoms do not pose significant health risks. Subjects who participate in this study will be asked to quit smoking on an assigned quit date. The smoking abstinence may result in increased irritability, anxiety, tension, depression, increased hunger or drowsiness.

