*a. Recruitment and Informed Consent.* Subjects will be recruited via metro mass media advertisements (television, radio, print, email, and internet). Those who see the mass media advertisements will contact Tobacco Research Programs in response to advertisements. Each subject interested in participating will be screened by telephone interview for eligibility. If eligible, subjects will be asked to attend a screening visit. At this visit subjects are provided with a detailed explanation of the study purpose and procedures (including risk involved), any questions a subject may have will be answered, subjects will be asked questions to assess their understanding of the study, and informed consent will be obtained before any study procedures are completed.

*b. Protection against Risk.* Subjects will be told the potential risks involved in this study. Although risks to subjects in

the proposed study are minimal, the following actions will be taken to minimize these risks. We will exclude subjects with health conditions that may be exacerbated by their participation. Subjects will be monitored regularly by medical personnel employed by the study. [name] (PI) will be available for emergency phone calls 24 hours/day and for office visits in case of problems. Blood will be collected by trained phlebotomists to reduce the risks involved with blood draws.

During generic Prometrium administration, the first dose of the study medication will be taken at 8 PM to minimize possible sedation from initiation of progesterone treatment. Subjects will be warned about using caution when driving a motor vehicle or operating machinery. Subjects will also be warned about the side effects associated with generic Prometrium. Further, although unlikely, the study physician ([name], PI) will be alert to the earliest manifestations of thrombotic disorders including thrombophlebitis, cerebrovascular disorders, pulmonary embolism, and retinal thrombosis (PDR, 2002). If any of these occur or are suspected, the study medication will be discontinued immediately and medical treatment will be sought.

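### Thrombotic events that stop study drug but are not fatal, life-threatening, disabling or hospitalised have no prompt reporting path

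*Combined protocol and SAP*

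**What the plan says.** The relevant text is in the DSMP, Sections E (Regulatory Issues), F (Trial Safety) and H (Data Safety and Monitoring Plan, Board, and Administration).

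- **Definition (Section E).** "A serious adverse event is defined as an outcome that is 1) fatal or life-threatening, 2) significantly or permanently disabling or incapacitating", then "3) requires or prolongs inpatient hospitalization, or 4) results in" a congenital anomaly. No diagnosis is named, and there is no further criterion for medically important events. Every adverse event is screened against this list: "All AEs will be assessed to determine if they meet criteria for an SAE".
- **Serious route (Sections E and H).** "SAE's, whether or not related to study medication, will be reported to the IRB and NIDA". The IRB, NIDA and FDA are telephoned within three days, and a written report follows within ten. The head of the DSMB is also told of each SAE.
- **Non-serious route (Section E).** "All drug related adverse events of a non-serious nature are reported" to the IRB every quarter. No other recipient is named there.
- **Annual route (Section H).** The DSMB receives a blinded summary of all data each year. Its report, which includes a summary of adverse events, is passed to NIDA.
- **Thrombotic events (Section F).** After a background paragraph on stroke, coronary disease, venous thromboembolism and breast cancer under combined hormone replacement, the plan writes: "However, as a safety measure for these serious adverse events, we will exclude subjects with history of thrombophlebitis, deep vein thrombosis, pulmonary embolus". Under protection against risk, the study physician is to watch for the "earliest manifestations of thrombotic disorders including thrombophlebitis, cerebrovascular disorders, pulmonary embolism, and retinal thrombosis". The next sentence reads: "If any of these occur or are suspected, the study medication will be discontinued immediately and medical treatment will be sought".

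**The concern.** Section F treats thrombotic disorders as grave enough to exclude people with a history of them and to stop study drug on suspicion alone. Section E decides who hears about an event, and how fast, from its outcome only. An event can therefore trigger the immediate stop in Section F and still meet none of the criteria in Section E.

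What is at stake is timeliness of safety information. While one participant has been taken off drug for a thrombotic event, others continue and new ones start. NIDA, the FDA and the DSMB head need not have been told. Prior experience with this exposure is limited by the plan's own account: the protocol's Study Medication section describes earlier use as shorter than one month, against twelve weeks here.

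**Working it through.** The documents give no figure to reproduce. The check sets the sections side by side and follows a thrombotic event through the rules as written.

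| Thrombotic event | Status under Section E | Individual report | Aggregate report |
|---|---|---|---|
| (a) Fatal, life-threatening, disabling or incapacitating, or hospitalised | SAE | IRB, NIDA and FDA by telephone within 3 days and in writing within 10, whatever the relationship; DSMB head | Annual DSMB summary, to NIDA |
| (b) None of these, considered drug related | Non-serious | IRB, quarterly | Annual DSMB summary, to NIDA |
| (c) None of these, not considered drug related | Non-serious | None specified | Annual DSMB summary, to NIDA |

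Rows (b) and (c) are the gap. An uncomplicated thrombophlebitis or deep vein thrombosis managed without admission can fall there, and so can a suspected event for which drug is stopped. Screening every adverse event against the SAE criteria does not close the gap, because these events do not meet those criteria.

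Whether an event falls in row (b) or (c) depends on the relationship rating. Section E has four grades (none, unlikely, possible, probable) but does not say which of them count as drug related.

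**How many others are exposed during a delay.** Inputs:

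- Enrolment of about 6 per month (protocol, Recruitment).
- Dosing from 7 days before the quit date to the Week 11 visit (protocol, Table 1 and Study Medication): 7 + 11 × 7 = 84 days.
- Expected drop-out of about 25% (protocol, Sample Size & Power Analysis).
- Assumptions: every enrolled participant starts drug, and a month has 30.4 days.

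Results:

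- On study drug at any time with full retention: 6 × 84/30.4 = 16.6.
- If the whole 25% were lost at the start: 0.75 × 16.6 = 12.4.
- With 1:1 allocation, about 6 to 8 of these are on progesterone.
- New starters in one quarter: 6 × 3 = 18.
- Longest quarter: 92 days, so a quarterly report can come up to 92 − 3 = 89 days after the SAE deadline.

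These numbers describe how many people are on or starting drug during a delay. They do not estimate how many events will occur, and the documents give no event rate.

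**The case against.** The strongest reply is that Sections E and F do different jobs. The definition in Section E is based on outcome for every kind of event, so the absence of thrombosis by name is not an omission. The reference to serious events in Section F closes a background paragraph on postmenopausal women taking estradiol with a synthetic progestin. It explains the exclusion criteria and does not classify on-trial events. Stopping drug as a precaution is not a seriousness criterion, and the two can coexist. Internal oversight is also real: the research nurse assesses adverse events weekly with the study physicians, the project manager meets the coordinator and the investigator weekly, and the DSMB chair can call a special meeting.

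Most of this stands, and it rules out several stronger readings that a reader might infer:

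- *That the SAE definition leaves thrombotic events out.* It does not. Any that is fatal, life-threatening, disabling or hospitalised is an SAE, which could cover many pulmonary emboli, strokes and retinal thromboses.
- *That any thrombosis treated without admission takes the quarterly route.* It does not. The life-threatening and disabling criteria need no admission.
- *That such an event would be rated unlikely related and so go unreported.* Section F does say that natural progesterone is not known to cause thromboembolism, but it also tells the physician to be alert for it, and the scale includes possible and probable. The documents do not show how an event would be rated.
- *That NIDA and the DSMB would never hear of it.* They would, late and in aggregate, through the annual summary.

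What the reply does not answer is rows (b) and (c). Internal oversight and an optional special meeting are not a stated prompt report to the IRB, NIDA, the FDA or the DSMB head.

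**Conclusion.** The point holds in a narrow form. For a thrombotic event that leads to stopping study drug but is not fatal, life-threatening, disabling or hospitalised, the rules as written give a quarterly report to the IRB if it is considered drug related, and otherwise no individual report at all. This follows from the stated rule and not from missing detail.

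The practical size is small. People with a thrombotic history are excluded and few such events are expected. The benefit is in the speed of safety reporting; power, type I error and the efficacy estimate are untouched. The exposure figures rest on steady enrolment at the planned rate and on a quarterly report issued at the end of the quarter. It is a cheap improvement and does not suggest that the trial is unsafe as designed.

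The same looseness appears once more. The protocol's entry for the Columbia-Suicide Severity Rating Scale calls suicidal ideation an SAE on the strength of the product label, although Section E would not capture ideation as such.

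**What to change.** Reconcile DSMP Sections E and F with one sentence in Section E. It should say that thrombotic events for which study medication is stopped, confirmed or suspected, are reported on the existing SAE timeline to the IRB, NIDA, the FDA and the head of the DSMB, wherever they are treated and whatever the rated relationship. The list should be the disorders named under protection against risk in Section F, plus deep vein thrombosis, which Section F names among the excluded histories but not in that watch list.

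Word it as a reporting path and not as a new seriousness criterion, so that safety tables still count SAEs by the four outcomes. The use of SAE for suicidal ideation can be aligned with Section E in the same edit.

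The cost is one sentence and a few extra expedited reports, some for suspected events later ruled out. Dosing and the rule for stopping drug stay as they are.

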## **F. Trial Safety**

*Potential Risks and Benefits for Participants.* The potential risks for study subjects are minimal to moderate. Medical histories for all subjects will be reviewed prior to entry into the study and all subjects will be under medical supervision while in the study. Urine and breath samples will be obtained and should not present risk to the subjects. Blood samples will be obtained by trained phlebotomists. A minimal amount of blood will be collected (20cc) per collection. Blood drawing may result in slight discomfort, bruising, or there may be some soreness at the puncture site. In some cases there may be dizziness or fainting.

Generic Prometrium, a natural progesterone, is generally well tolerated. The most common adverse effect is sedation. Other less common adverse effects include menstrual irregularity, spotting or breakthrough bleeding, dizziness, cramps, nausea, fatigue, headache and breast tenderness (de Lignieres, 1999; Simon, 1995, Sofuglu, 2009). Other side effects attributed to synthetic progesterone, including depression, fluid retention, pruritus, jaundice, rash and thrombotic disorders, are unlikely to occur. Recently there have been reports of increased risk of stroke, coronary artery disease, venous thromboembolism and breast cancer in postmenopausal females who have been on long-term hormone replacement treatment with estradiol and progestin (medroxyprogesterone) combination (Anonymous, 2002; Grady et al., 2002; Hulley et al., 2002; Nelson et al., 2002). While some of these adverse events develop after years of treatment, venous thromboembolism is seen within the first year of treatment (Anonymous, 2002). It is possible that progestins may contribute to thromboembolism seen during estradiol and progestin treatment and thromboembolism is listed in the PDR as one of the adverse events for medroxyprogesterone treatment (PDR, 2002). In contrast to synthetic progestins, natural progesterone is not known to cause thromboembolism (PDR, 2002). However, as a safety measure for these serious adverse events, we will exclude subjects with history of thrombophlebitis, deep vein thrombosis, pulmonary embolus, clotting or bleeding disorders, heart disease, diabetes or history of stroke. Possible adverse events from generic Prometrium will be assessed weekly by the research nurse ([name], NP) in consultation with the study physicians ([name] MD, [name] MD). If the side effects cannot be tolerated the medication dosage will be decreased to 200 mg daily.

Although uncomfortable, withdrawal symptoms do not pose significant health risks. Subjects who participate in this study will be asked to quit smoking on an assigned quit date. The smoking abstinence may result in increased irritability, anxiety, tension, depression, increased hunger or drowsiness.

*a. Recruitment and Informed Consent.* Subjects will be recruited via metro mass media advertisements (television, radio, print, email, and internet). Those who see the mass media advertisements will contact Tobacco Research Programs in response to advertisements. Each subject interested in participating will be screened by telephone interview for eligibility. If eligible, subjects will be asked to attend a screening visit. At this visit subjects are provided with a detailed explanation of the study purpose and procedures (including risk involved), any questions a subject may have will be answered, subjects will be asked questions to assess their understanding of the study, and informed consent will be obtained before any study procedures are completed.

*b. Protection against Risk.* Subjects will be told the potential risks involved in this study. Although risks to subjects in

the proposed study are minimal, the following actions will be taken to minimize these risks. We will exclude subjects with health conditions that may be exacerbated by their participation. Subjects will be monitored regularly by medical personnel employed by the study. [name] (PI) will be available for emergency phone calls 24 hours/day and for office visits in case of problems. Blood will be collected by trained phlebotomists to reduce the risks involved with blood draws.

During generic Prometrium administration, the first dose of the study medication will be taken at 8 PM to minimize possible sedation from initiation of progesterone treatment. Subjects will be warned about using caution when driving a motor vehicle or operating machinery. Subjects will also be warned about the side effects associated with generic Prometrium. Further, although unlikely, the study physician ([name], PI) will be alert to the earliest manifestations of thrombotic disorders including thrombophlebitis, cerebrovascular disorders, pulmonary embolism, and retinal thrombosis (PDR, 2002). If any of these occur or are suspected, the study medication will be discontinued immediately and medical treatment will be sought.

There may be risk to confidentiality and privacy of study data. To minimize this risk, subjects will be assigned unique three-digit identification numbers. The questionnaires and study samples will retain only the unique study number. These numbers will be linked to the subject's identifier information in a database separate from assay results or other data collected. The database requires at least 2 levels of security (i.e., passwords), which will allow only authorized research team members to access the information.

#### Potential Benefits of the Proposed Research to the Subjects and Others

Whereas no assurance can be made to an individual subject that he/she will personally benefit from such research, the experience should be beneficial. Subjects will have the opportunity to learn about their smoking behavior and receiving smoking cessation behavioral counseling. Society may benefit from a better understanding of the role of sex and sex hormones on smoking behavior and impulsivity. A better understanding of this relationship will help improve treatment strategies for nicotine dependence. The risks in relation to the potential benefits are minimal to the individual research subject and virtually nonexistent to society in general.

#### **G. Trial Efficacy**

No interim analyses of efficacy are planned for the proposed study.

#### **H. Data Safety and Monitoring Plan, Board, and Administration.**

The Service Core ([name], Director) of the P50 will implement the plans and organize review by the Data Safety and Monitoring Board (DSMB). The Service Core (B) will administratively oversee the DSM Plan, Board and complying with reporting requirements. This provides additional separate attention to, monitoring and focus on safety. The DSMB will meet annually and will, post meeting, provide a summary of discussion, which will be conveyed to NIDA. This report will include subject demographics, expected versus actual recruitment rates, summary of any quality assurance or regulatory issues, summary of adverse events (AEs) or serious adverse events (SAEs) which may have occurred, and any changes in the protocol as a result of these issues. The DSMB will receive current data and blinded data unless a specific request or cause to view unblinded data is evident. The final report will be complete and inclusive with the unblended data set.

The Service Core Project Manager ([name]) will meet with the Study Coordinator ([name]) and PI ([name]) on a weekly basis to review the study's progress. Additionally, the Service Core Director ([name]) will also be available to identify and solve problems in the study's implementation, as well as advise on any adverse events experienced by subjects during the study. Drs. [name], [name] (PI Project 1) and [name] (PI Project 2) will meet regularly and as needed regarding data and project safety. Additionally, all key personnel will meet regularly regarding overall progress, specific problems and problem resolution. The daily monitoring of subjects will be the coordinator's responsibility. The coordinator will also report to the Project Manager and PI as needed.

Participants will be closely monitored throughout the trial. A summary of all data, with the exception of information that entails breaking the blind, will be provided to the DSMB at annual meetings. SAE's will be reported to the head of the DSMB when they have been identified and characterized. The chair of the DSMB may request a special meeting of the panel as needed. The Board will consist of Drs. [name], [name] and [name]. These individuals will serve to monitor SCOR projects involving human subjects.

The group will meet on an annual basis and review data including recruitment, progress, safety, adverse events, and serious adverse events associated with the study. The DSMB meeting will include open, closed and executive

sessions. The Principal Investigator, co-investigators, and statisticians will attend the open session and present during the meeting. The purpose of the open session is to provide relevant information to the Board about general aspects of the trial. The open session will focus on the background of the study, the protocol, status of the study, problems with accrual and follow-up, baseline demographic data, compliance issues, frequency of adverse events, documentation of endpoints, data quality issues, flow of forms, data based protocol modification issues, and any other issue regarding the studies under review that can be discussed without reference to interim comparative results.

Following the open session, a closed session will be held. During the closed session, the chairperson ([name] MD) will conduct the review of all issues and puts each issue to a vote. This session will be attended by the DSMB members and if necessary the statistician, principal investigator. During the closed session, the discussions will focus on the treatment safety, requesting and reviewing additional information if needed and updating the Board on actions taken related to their actions and recommendations of the previous meeting.

Following the closed session, an executive meeting may be held. The executive meeting will be restricted to DSMB members. During these sessions, the Board may discuss any sensitive issues surrounding the clinical trials under review.

The Board Chairperson will prepare a draft report of the meeting along with minutes for inclusion in the final DSMB report. The report will outline and summarize discussion during the open and closed sessions of the meeting. Recommendations and action items will be clearly marked within the body of the report. If the DSMB conducts an executive session, a statement will be included in the Minutes of the Meeting stating that an executive session was conducted, but content of the discussion will be retained by the chair and not included in the report. The draft report shall be reviewed and edited by all Board members prior to issuance of the final report.

